11.2.2. Subject Populations for Analysis

The following analysis populations will be defined for this study:

Intent-to-Treat: will include any subject randomized into the study that receives a dose of study drug and that has completed at least one post-baseline efficacy measurement while on study medication;

Safety: Any subject randomized into the study that receives a dose of study drug;

Per-Protocol: Any subject who is randomized and receives the protocol required study drug exposure and required protocol processing.

Efficacy analyses will be performed on the Intent-to-Treat population and the Per-Protocol population. Safety summaries will be based on Safety set. Subject characteristics will be presented for all subjects randomized.

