**SIGNATURE PAGE FOR VANDA PHARMACEUTICALS INC.**

**Amendment No. 6 to VP-VLY-686-3301**

Approved by the following:

Program Lead:

*[name]*

12/12/2022 | 5:04 PM EST

\_\_\_\_\_  
[name]

\_\_\_\_\_  
Date

Senior Vice President, Research &  
Development Committee

Medical Director:

*[name]*

12/12/2022 | 5:02 PM EST

\_\_\_\_\_  
[name].

\_\_\_\_\_  
Date

Medical Director

Name of Sponsor/Company: Vanda Pharmaceuticals Inc.	
Name of Investigational Product: Tradipitant (VLY-686)	
Name of Active Ingredient: {2-[1-(3,5-Bistrifluoromethylbenzyl)-5-pyridin-4-yl-1H-[1,2,3]triazol-4-yl]-pyridin-3-yl}-(2-chlorophenyl)-methanone	
Title of Study: A Multicenter, Randomized, Double-Blind, Placebo-Controlled Phase III Study to Assess the Efficacy of Tradipitant in Relieving Symptoms of Gastroparesis	
Study center(s): Approximately 50 centers in the United States	
Indication: Diabetic & Idiopathic Gastroparesis	Phase of development: III
Number of subjects (planned): Up to 800 subjects will enroll in the study. Group 1: Approximately 200 gastroparesis subjects will be determined eligible to enter the Evaluation Phase and be randomized to one of 2 arms (100 per arm, 1:1 randomization scheme). Group 2: Up to 600 gastroparesis subjects that are not eligible to be randomized will enter into the 12 week Open Label Phase of the study.	

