16. Surgeries to the stomach including gastrectomy, fundoplication, vagotomy, pyloroplasty, bariatric surgery excluded in Group 1 and excluded in Group 2 if performed < 2 months from screening . Additionally, gastric stimulation device surgically implanted within the last year or if implanted more than a year ago for Group 1 subjects or withing the last 2 months for Group 2 subjects, or have changed stimulation settings within the last 3 months (ie gastric stimulation device must have a stable setting for at least 3 months) for Group 1 and withing the last 1 month for Group 2 subjects
17. Use of prohibited medication or medication with anti-nausea, antiemetic, neuromodulating, or prokinetic effect within 2 weeks of the screening visit EXCEPT when administered on a stable daily dosing schedule (stable for at least 3 months prior to the screening visit) or administered under protocol-specified rescue medication guidelines;
18. Use of the following within 2 weeks of screening: another NK-1 antagonist or a second generation 5-HT3 antagonist for Group 1 and Group 2, phenergan more than 2 times per day for Group 1 only, or opioids more than 2 times per week for Group 1 only;
19. Pyloric injection of neurotoxins (e.g. botulinum type A or B) within 3 months of the Screening Visit for Group 1 or within 1 month of Screening for Group 2;
20. Exposure to any investigational medication, including placebo, within 60 days of the Baseline Visit;

21. Patients who previously participated in study VP-VLY-686-2301 or any other clinical study of tradipitant in the past.

Investigational product, dosage and mode of administration:
 
Group 1: Oral 85 mg tradipitant and matching placebo capsules will be administered. Subjects will be randomized to one of two treatment arms to receive 85 mg tradipitant BID or placebo.
 
Group 2: Open label Oral 85 mg tradipitant capsules will be administered to all group 2 patients.
 
All subjects will be instructed to take 1 capsule in the morning and another approximately 12 hours later in the evening.

Duration of treatment: Up to 12 weeks

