
Objectives:
 
Primary:
 

• To evaluate the efficacy of tradipitant relative to placebo in change from baseline to Week 12 in the daily nausea severity scores.

 
Secondary:
 

• To evaluate the efficacy of tradipitant relative to placebo in change from baseline in number of days at “0” nausea.

• To evaluate the efficacy of tradipitant relative to placebo in change from baseline of other individual symptoms associated with gastroparesis.

• To evaluate the efficacy of tradipitant relative to placebo in change from baseline of the overall symptom burden associated with gastroparesis.

• To evaluate the efficacy of tradipitant relative to placebo in change from baseline of global improvement and quality of life measures.

• To explore the safety and tolerability of multiple oral doses of tradipitant.

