
Overall Design:
 
This is a multicenter, randomized, double-blind, placebo-controlled study to be conducted in the United States. Up to eight hundred (800) subjects diagnosed with gastroparesis, who satisfy the selection criteria for the study, will be eligible for one of two groups. Group 1 will enter the Evaluation Phase of the study and Group 2 will enter the Open Label phase of the study. Patients eligible for Group 1 will be randomized to one of two treatment groups. Randomization will be stratified by disease etiology (idiopathic or diabetic), and enrollment for either of the etiologies will be capped at 60% of the total sample size. Patients eligible for Group 2 will enter the Open Label Phase of the study.
 
The study includes two phases: the screening phase and the evaluation phase. The screening phase includes a screening visit to evaluate subjects’ preliminary eligibility for the study. During the screening phase, subjects will collect diary data for at least 4 weeks. The data collected during the screening phase must be reviewed in order to determine eligibility for enrollment into the evaluation phase. Data review will be performed prior or at Visit 2. Patients who to meet all Group 1 eligibility criteria will randomized onto double blind treatment in the evaluation phase. Patients who meet Group 2 criteria or do not meet symptom criteria for randomization but still meet all other eligibility criteria, will be offered open label treatment in the open label arm of the evaluation phase. When enrollment goal is reached for

group 1, group 1 enrollment will be closed and all subsequent patients in screening will be evaluated for group 2 eligibility only.

The Evaluation Phase includes 12 weeks of double blind randomized treatment of placebo or tradipitant (85mg bid, approximately 12 hours apart) for Group 1 or open label tradipitant (85mg bid, approximately 12 hours apart) for Group 2. Daily diaries will be completed during all phases. Clinical evaluations and safety assessments will occur at Screening, Baseline, Week 2, Week 4, Week 6, Week 8, Week 10, and Week 12.

Following the End of Study Visit (Visit 8) patients can opt-in to a one-day optional pharmacokinetic (PK) study where one additional dose of tradipitant will be taken and blood will be drawn pre-dose and, 1, 2, 4, 6, 8-hour post dose to assess drug levels. This optional PK Visit can occur 1-14 days after Visit 8.

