11.2. Statistical Methods and Analysis Plan

This section describes the planned statistical analyses in general terms. A complete description of the methodology will be specified in a statistical analysis plan (SAP). Any changes in the statistical methods described in this protocol that occur prior to database lock will be documented in the SAP and will not require a protocol amendment.

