11.2.3. Subject Disposition

Study completion and reasons for discontinuation for all randomized subjects in the double-blind phase will be summarized for each treatment group. Discontinuations by reason will be tabulated by visit for each treatment group.

Time to discontinuation due to adverse events, lack of efficacy and for any reason will be analyzed using Kaplan-Meier survival techniques; the log-rank test will be used for group comparison.

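### The Safety set admits only randomized subjects and no all-treated set is named, so the safety summaries as written omit open-label Group 2: up to 600 of the 700 patients assigned to 12 weeks of tradipitant

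*SAP*

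**What the plan says.** SAP Section 11.2.2 names three analysis populations: Intent-to-Treat, Safety and Per-Protocol. All three require randomization. The Safety definition is "Safety: Any subject randomized into the study that receives a dose of study drug", and the section adds that "Safety summaries will be based on Safety set".

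The protocol synopsis describes a second group that is never randomized. Under the planned number of subjects: "Up to 600 gastroparesis subjects that are not eligible to be randomized will enter into the 12 week Open Label Phase". Under investigational product: "Open label Oral 85 mg tradipitant capsules will be administered to all group 2 patients". The Overall Design paragraph gives the regimen as "open label tradipitant (85mg bid, approximately 12 hours apart) for Group 2".

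One of the secondary objectives is "To explore the safety and tolerability of multiple oral doses of tradipitant". It is not limited to Group 1.

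Other parts of Section 11 follow the same pattern. Section 11.2.3 begins: "Study completion and reasons for discontinuation for all randomized subjects in the double-blind phase will be summarized for each treatment group". Section 11.2.4 presents demography for randomized subjects, and Section 11.2.6 tabulates medications in the Safety Population. Sections 11.4 to 11.4.5, on safety, name no other set. Nowhere does Section 11 mention Group 2, an open-label phase or an all-treated set.

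**The concern.** A randomized-only set is the right basis for comparing tradipitant with placebo. The difficulty is that it is the only safety set, in a study where most of the planned exposure to tradipitant is open label. A programmer who followed Section 11.2.2 exactly would produce adverse event, SAE, laboratory, vital sign, ECG, C-SSRS and concomitant medication tables without a single Group 2 patient.

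The safety objective would then rest on about 100 patients assigned to tradipitant, and these may not represent the others. Group 2 accepts HbA1c up to 11, against 9 in Group 1 (exclusion criterion 15). It admits post-surgical and viral etiologies (inclusion criterion 11). It is also exempt from the opioid-frequency limit in exclusion criterion 18. A safety signal confined to such patients would not show in any planned summary.

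**Working it through.** **Who can enter the Safety set**

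1. Membership needs two things: randomization and at least one dose (SAP Section 11.2.2).
2. Group 2 patients are dosed but are not randomized (synopsis, planned number of subjects and Overall Design).
3. So no Group 2 patient can be a member. Reading randomized loosely as enrolled does not work, because the synopsis contrasts the two groups on exactly this point.

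**Which outputs are affected**

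| SAP section | Output | Set named | Group 2 |
|---|---|---|---|
| 11.4 to 11.4.5 | AE, SAE, laboratory, vital sign, ECG and C-SSRS summaries | Safety set, through 11.2.2 | Excluded |
| 11.2.6 | Prior and concomitant medication | Safety Population | Excluded |
| 11.2.3, first sentence | Completion and reasons for discontinuation | Randomized, double-blind phase | Excluded |
| 11.2.3, later sentences | Discontinuations by visit; time to discontinuation | None | Unclear |
| 11.2.4 | Demography | Randomized | Excluded |
| 11.2.4 | Medical history | None, though conditions are dated from randomization | Unclear |
| 11.2.5 | Visit counts; compliance | None | Unclear |
| 11.2.5 | Significant noncompliance | Double-blind phase | Excluded |
| 11.4.4, 11.4.5 | ECG and C-SSRS listings by subject | None | May be included |

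**Head count**

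Inputs, all from the synopsis: Group 1 has about 200 patients, 100 per arm; Group 2 has up to 600; the total is up to 800. The total reproduces: 200 + 600 = 800.

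Assigned to 12 weeks of tradipitant: 100 + 600 = 700. This counts 12-week assignments. Placebo patients who opt into the pharmacokinetic visit after Visit 8 may take one tradipitant dose and are not counted here.

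Share of these patients outside the Safety set, with n₂ the number enrolled in Group 2: n₂ / (100 + n₂).

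| n₂ | Calculation | Outside the Safety set |
|---|---|---|
| 600 (planned maximum) | 600/700 | 85.7% |
| 300 (assumption) | 300/400 | 75.0% |
| 100 (assumption) | 100/200 | 50.0% |

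Among all dosed subjects at the maximum, placebo included, 600/800 = 75% are outside and 200/800 = 25% inside. Both counts assume that everyone enrolled is dosed.

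**What the missing patients are worth**

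For an event seen zero times in N patients, the one-sided 95% upper bound on its rate is 1 − 0.05^(1/N):
- N = 100: 2.95%
- N = 700: 0.43%

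The chance of seeing at least one event whose true rate is 0.5% is 1 − 0.995^N:
- N = 100: 39%
- N = 700: 97%

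These figures assume one common rate in both groups. They show scale only, since the groups may differ.

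**The case against.** The strongest reply is that Section 11 is not the full plan. Section 11.2 says that it describes the analyses in general terms and leaves the complete methodology to a separate SAP. Listing three populations does not rule out a fourth. That SAP was not available and could contain the missing set, so it cannot be said that Group 2 safety will go unsummarized. This stands as a limit on the claim. It does not remove the problem: Section 11.2.2 is not silent but gives an explicit rule, and nothing in Section 11 promises an open-label set.

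Second, the protocol is loose about randomization. The contraception rules in inclusion criterion 5 apply to both groups yet are timed from randomization, which suggests wording never updated for Group 2 and not a decision to exclude it. That may well explain the gap, but it cannot override the plain statement that Group 2 is not eligible to be randomized.

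Third, 600 is a maximum with no stated minimum, so 85.7% is the upper end. That is correct, and the range is shown above. The number left out changes; the exclusion of all of Group 2 does not.

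Fourth, the impact is bounded. The safety objective is exploratory, the data will be collected, and listings may carry them. The opioid example concerns exclusion criterion 18 alone; criterion 17 also restricts prohibited medication, and that list is not in the documents. These points bear on how serious the gap is, not on whether it exists.

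**Conclusion.** The concern holds for Section 11 as written. The safety summaries exclude every Group 2 patient: at the planned maximum, 600 of the 700 assigned to 12 weeks of tradipitant (85.7%), and still half if Group 2 reached only 100. The summary of completion and discontinuation reasons and the demography tables are closed to Group 2 as well; several others name no set and are ambiguous.

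The conclusion rests on the literal definition in Section 11.2.2 and on the absence of any other set in Section 11. It would fall away if the separate SAP defines an all-treated or open-label set. The tradipitant-placebo comparison in Group 1 and all efficacy analyses are untouched. This should be fixed before database lock, and confidence in the reading of the text is high.

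**What to change.** 1. Keep the randomized Safety set for the Group 1 comparison between arms.
2. Add a set along these lines: *All-Treated set: any subject, randomized or open label, who receives at least one dose of study drug.* Report Group 2 safety in its own column, because its population differs. Add a pooled tradipitant column (Group 1 tradipitant arm plus Group 2, by 12-week assignment) as a descriptive supplement, with no test against placebo. The separate Group 2 column is the essential part.
3. Extend the disposition, baseline, exposure and compliance, and concomitant medication tables to Group 2. State the set for the summaries that now name none: medical history (Section 11.2.4), visit counts and compliance (Section 11.2.5), and the later sentences of Section 11.2.3.

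The cost is a few lines of SAP wording and extra table columns, with no new data and no new patients. Section 11.2 lets changes in statistical methods made before database lock be documented in the SAP without a protocol amendment; an added analysis set would reasonably count as such a change, though the section does not say so expressly. If the separate SAP already has the set, aligning Section 11.2.2 with it is enough.

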11.2.3. Subject Disposition

Study completion and reasons for discontinuation for all randomized subjects in the double-blind phase will be summarized for each treatment group. Discontinuations by reason will be tabulated by visit for each treatment group.

Time to discontinuation due to adverse events, lack of efficacy and for any reason will be analyzed using Kaplan-Meier survival techniques; the log-rank test will be used for group comparison.

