11.2.1. General

Statistical analyses will be performed using two-sided tests.

Data will be summarized by treatment group (and by visit when applicable), with respect to demographic and baseline characteristics, efficacy variables, and safety variables.

Summary statistics will include the mean, N, standard deviation, median, minimum, and maximum values for continuous variables, and frequencies and percentages for categorical variables.

Continuous efficacy variables will be analyzed using a mixed-effect model for repeated measures (MMRM) and/or an analysis of covariance (ANCOVA) model. The models will be described in the SAP.

For the analyses of change from baseline, only subjects with a baseline and at least one (1) post-baseline measure will be included in the analysis. Unless otherwise specified, baseline is defined as the latest non-missing observation across all the visits in the screening phase, before the active study drug begins. Endpoint will be the latest non-missing observation across all the post-baseline visits in the evaluation phase.

Low enrolling sites will be pooled for analysis and the pooling algorithm will be determined prior to breaking the blind. The goal of pooling low enrolling sites is to have a sufficient number of subjects per treatment group within a site for the analysis models and for the evaluation of the treatment-by-site interaction for the primary endpoint. Unless otherwise specified, the pooled sites will only be used in the analyses where site is included. The actual sites rather than the pooled sites will be specified in data listings.

Categorical variables will be analyzed using the Cochran-Mantel-Haenszel (CMH) test blocking on sites, and Fisher's exact test will be used when site is not adjusted (mainly for safety assessment).

Details of the model and the analyses will be specified in the SAP. All statistical analyses will be performed using SAS®, Version 9.1.3 or higher.

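### Kaplan-Meier curves for stopping due to adverse events or lack of efficacy, if read as probabilities, overstate each reason; cumulative incidence curves should be shown instead

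*SAP*

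**What the plan says.** SAP section 11.2.3 (Subject Disposition) sets the method for three time-to-event outcomes: "Time to discontinuation due to adverse events, lack of efficacy and for any reason will be analyzed using Kaplan-Meier survival techniques". For the arms, "the log-rank test will be used for group comparison". It does not say how a subject who leaves for a different reason enters the adverse-event or lack-of-efficacy curve, and it names no competing-risks method.

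The same section also plans crude summaries: "Study completion and reasons for discontinuation for all randomized subjects in the double-blind phase will be summarized for each treatment group", and "Discontinuations by reason will be tabulated by visit for each treatment group". Section 11.4.1 adds the proportion of subjects in each arm with adverse events that led to discontinuation.

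Section 11.2 describes the methods as general and leaves the full methodology to a separate statistical analysis plan, which is not among the documents. No dropout rate, overall or by reason, appears in either document.

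**The concern.** Reasons for stopping exclude one another. Kaplan-Meier knows only two states, event or censored, so a curve for one reason must censor those who left for another unless a special rule is written. With that censoring, one minus Kaplan-Meier describes a setting in which the other reasons do not operate. It never falls below the share of randomized subjects who actually stop for that reason, and it lies above that share once other dropout precedes an event.

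Two things are at stake, both modest. First, the report could carry two different Week 12 figures for what readers will take to be one quantity: the Kaplan-Meier estimate and the crude proportion. Second, a reader who compares the two arms' curves as probabilities could see a tolerability gap that comes only from unequal dropout for other reasons.

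The reading as a setting without the other reasons also needs independent causes. Section 11.4.1 counts worsening from baseline as treatment-emergent, so worsening nausea could plausibly be recorded either as an adverse event or as lack of efficacy. Independence is therefore not obvious here.

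**Working it through.** **Inputs from the documents.** Method: Kaplan-Meier with log-rank (SAP 11.2.3). Arm size: "100 per arm, 1:1 randomization scheme" (Protocol synopsis, number of subjects). Follow-up: "The Evaluation Phase includes 12 weeks of double blind randomized treatment" (Protocol synopsis, overall design). Sidedness: "Statistical analyses will be performed using two-sided tests" (SAP 11.2.1). There is no planned discontinuation figure to reproduce.

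**Assumptions.** Other reasons are censored. Hazards are constant over 12 weeks. At Week 12 the reason of interest accounts for 3% to 15% of subjects and all other reasons for 5% to 30%. The log-rank test uses a 5% level, which the documents state only for the sample size.

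**Step 1: formula.** Let F1 be the true cumulative incidence of the reason and F2 that of all other reasons. The total cumulative hazard is −ln(1 − F1 − F2), and the share F1/(F1 + F2) belongs to the reason of interest. Hence

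1 − KM = 1 − (1 − F1 − F2)^(F1/(F1+F2)).

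Example: F1 = 10%, F2 = 20% gives 1 − 0.70^(1/3) = 11.2%.

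**Step 2: overstatement at Week 12.**

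| True F1 | Other F2 | 1 − KM | Excess (points) |
|---|---|---|---|
| 3% | 5% | 3.1% | 0.1 |
| 5% | 15% | 5.4% | 0.4 |
| 5% | 25% | 5.8% | 0.8 |
| 10% | 20% | 11.2% | 1.2 |
| 10% | 30% | 12.0% | 2.0 |
| 15% | 25% | 17.4% | 2.4 |

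The relative excess runs from about 3% to 20%. Putting both upper ends together (15% and 30%, so 45% total dropout) gives 1 − 0.55^(1/3) = 18.1%, an excess of 3.1 points.

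**Step 3: arms compared as probabilities.** True adverse-event incidence is 10% in both arms.
- Other dropout 5% versus 20%: 1 − KM is 10.3% versus 11.2%, a gap of 0.9 points.
- Other dropout 5% versus 30%: 10.3% versus 12.0%, a gap of 1.7 points.

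For scale, the standard error of a difference between two 10% proportions with 100 per arm is √(2 × 0.10 × 0.90 / 100) = 4.2 points.

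**Step 4: log-rank test.** This was checked by simulation: 20,000 trials, 100 per arm, independent exponential causes, other reasons censored, two-sided 5%.
- Equal adverse-event hazards (0.10 over the 12 weeks), other-reason hazards 0.10 versus 0.30: rejects in 5.0% of trials.
- Equal adverse-event hazards (0.10), other-reason hazards 0.05 versus 0.40: 4.8%.
- Equal adverse-event incidence of 10%, other dropout 5% versus 30%: 6.5%. Here the adverse-event hazards differ (0.108 versus 0.128), so this is not an inflated error rate for a test of hazards.

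**Step 5: any-reason curve.** It has no competing reason, so F2 = 0 and the formula returns F1. There is no excess.

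**The case against.** The strongest reply is that the plan already delivers the right percentages. Follow-up is a fixed 12 weeks. If every early exit has a recorded reason, there is essentially no administrative censoring, and the crude proportion by reason equals the Aalen-Johansen estimate at Week 12. Sections 11.2.3 and 11.4.1 both plan such proportions, and nothing says that percentages will be read off the Kaplan-Meier curves. This stands. It confines the point to the two plotted curves and any estimates taken from them, but it leaves those curves in conflict with the tables beside them.

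It is also fair to say that each estimator answers its own question. Suppose the adverse-event hazards are equal, with a net probability of 10% in each arm, and net lack-of-efficacy dropout is 5% versus 20%. Kaplan-Meier then agrees across arms. Cumulative incidence does not: 0.1054/(0.1054 + 0.0513) × (1 − 0.90 × 0.95) = 9.8%, against 0.1054/(0.1054 + 0.2231) × (1 − 0.90 × 0.80) = 9.0%. Under independent causes, Kaplan-Meier is a legitimate display of cause-specific hazards. This stands too, and it is why the display needs a label and the log-rank test can stay.

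The censoring rule is inferred, and the separate analysis plan may state one. That also stands. Still, section 11.2.3 already names the method and, unlike sections 11.3.2, 11.4.1, 11.4.2 and 11.4.5, carries no deferral of its own.

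A reader might infer more than the documents support:
- **That the cause-specific curves must add up to more than the any-reason curve.** Only two such curves are planned. With true rates of 8% (adverse events), 10% (lack of efficacy) and 12% (other), they read 9.1% + 11.2% = 20.3%, below the any-reason 30%. The sum reaches 33.6% only if an unplanned 13.3% curve for other reasons is added.
- **That the planned arm comparison is invalid.** That comparison is the log-rank test, and step 4 shows that it keeps its size for cause-specific hazards.
- **That the result is tilted towards tradipitant.** That requires more lack-of-efficacy dropout on placebo, which the documents neither state nor assume.

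**Conclusion.** The point holds in a limited form. If other reasons are censored, one minus Kaplan-Meier for adverse-event or lack-of-efficacy discontinuation overstates the probability of stopping for that reason. The excess is about 0.1 to 2.4 points at Week 12 over the tabulated pairings, and about 3 points at the extreme corner. Arms with the same true incidence can appear 1 to 2 points apart. These sizes rest on assumed dropout rates, constant hazards and an inferred censoring rule. The direction of any gap between arms cannot be known in advance.

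The gap is small beside sampling error at 100 per arm, and it sits in a supportive disposition analysis. This is a worthwhile minor improvement and does not threaten the trial's conclusions.

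**What to change.** In section 11.2.3, or in the separate analysis plan:

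1. Keep Kaplan-Meier and the log-rank test for discontinuation for any reason.
2. For discontinuation due to adverse events and due to lack of efficacy, present Aalen-Johansen cumulative incidence curves by arm, with all other reasons as competing events.
3. Keep the log-rank test for these two reasons, state that other reasons are censored in it, and label it a comparison of cause-specific hazards.

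The curves should then agree with the by-reason tables at Week 12, apart from any administrative censoring. The cost is one or two sentences and a little extra programming, with no new data. Section 11.2 lets changes in method made before database lock be documented in the analysis plan without a protocol amendment.
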